5.6. SAFETY ANALYSIS SET [SAF]

The safety analysis set (SAF) will contain all patients who receive at least one dose of study medication (or part thereof).

If there is any doubt whether a patient was treated or not, they will be assumed treated for the purposes of analysis.

5.7. TROUGH PK ANALYSIS SET [TROUGH PK SET]

The trough PK analysis set (Trough PK set) will contain all patients who received at least one dose of study medication and have at least one valid measured trough F901318 plasma concentration. A valid trough sample should include date, time and trough value.

5.8. INTENSIVE PK ANALYSIS SET [INTENSIVE PK SET]

The intensive PK analysis set (Intensive PK set) will consist of the subset of patients in the SAF population who have an evaluable intensive PK profile from which at least one PK parameter can be determined.

6. GENERAL CONSIDERATIONS

Analyses will generally be descriptive in nature with efficacy data presented overall and by Baseline DRC-adjudicated disease category using appropriate summary statistics. Safety data will be presented overall only. Categorical data will be described using absolute and relative frequencies (n and %). Percentages will be presented to 1 decimal place. Continuous data other than PK will be presented using descriptive statistics (n, mean, standard deviation [SD], minimum, median and maximum). The precision of the measurement for each continuous variable will be used to determine the number of decimal places to present in tables, figures and listings, as specified in [appendix 1](#). Minimum and maximum values will be reported with the same precision as the unit of measure. For detail on PK data presentation refer to [Section 17](#).

Document: \\ieedc-vnasc01\BIOSdata\F2G\F901318 [REDACTED]
Author: [REDACTED] Version Number: 3.0
Version Date: 06Apr2023
Template No.: CS_TP_BS016 Revision 6 Reference: CS_WI_BS005
Effective Date: 02Dec2019

F2G Ltd.
PROTOCOL F901318/0032

Relevant raw and derived variables will be listed in individual by-patient data listings, sorted by Baseline DRC-adjudicated disease category, centre and patient number.

6.1. REFERENCE START DATE AND STUDY DAY

Reference start date is defined as the date of the first dose of study medication, (Day 1 is the day of the first dose of study medication).

Study Day will be calculated from the reference start date and will be used to show start/stop day of assessments and events. Study Day will appear in every listing where an assessment date or event date appears.

- If the date of the event is on or after the reference date, then:

$$\text{Study Day} = (\text{date of event} - \text{reference date}) + 1.$$

- If the date of the event is prior to the reference date, then:

$$\text{Study Day} = (\text{date of event} - \text{reference date}).$$

In the situation where the event date is partial or missing, the date will appear partial or missing in the listings, and Study Day, and any corresponding durations will be presented based on the imputations specified in [appendix 2](#); Partial Date Conventions.

6.2. BASELINE

Unless otherwise specified, Baseline is defined as the last non-missing measurement (including unscheduled measurements) taken up to and including Day 1 prior to first administration of study medication. In the case where the last non-missing measurement and the reference start date coincide, collection time, where available, will be compared with the first dose time to determine whether the measurement is pre-baseline or post-baseline. If time is not available or if assessment time coincides with reference start time, the measurement will be considered pre-baseline, but adverse events (AEs), medications and non-medication procedures commencing on the reference start date will be considered post-baseline.

6.3. DERIVED TIMEPOINTS

Derived EOT

Document:	\\ieedc-vnasc01\BIOSdata\F2G\F901318\		
Author:		Version Number:	3.0
		Version Date:	06Apr2023
Template No.:	CS_TP_BS016 Revision 6	Reference:	CS_WI_BS005
Effective Date:	02Dec2019		

F2G Ltd.
PROTOCOL F901318/0032

For patients that reach their Day 84 visit while still on treatment (also considered the EOT visit), data may not be entered on both Day 84 and EOT eCRF pages. Therefore, a derived EOT assessment will be determined in order that all patients are included in summaries for EOT visit.

Derived EOT visit is defined as the last non-missing measurement (including unscheduled measurements) which started after the first study medication administration up to and including the last study medication administration on the main study phase.

Derived Day 84

Similarly to above, for all efficacy endpoints at Day 84 visit, patients data may not be entered on both Day 84 and EOT eCRF pages. Therefore derived Day 84 efficacy response will be determined for responses entered in the Day 84 window, similar to derived EOT, so that patients will be presented in summary tables at both Derived Day 84 and Derived EOT.

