6.4. RETESTS, UNSCHEDULED VISITS AND EARLY TERMINATION DATA

In general, for by-visit summaries, data recorded at the nominal visit will be presented. Unscheduled measurements will not be included in by-visit summaries but will contribute to the derived EOT/EOS value, or best/ worst case value where required (e.g. shift table).

In the case of a retest (same visit number assigned), the latest available measurement for that visit will be used for by-visit summaries.

Listings will include scheduled, unscheduled, retest and early discontinuation data.

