6.5. WINDOWING CONVENTIONS

Visit windows are assigned based on the

Protocol SOA are presented in below table. Assigned Visit

SOA day(s)	Study day(s)
V1 (Screening)	-7
V2 (Treatment)	1

Document: \\ieedc-vnasc01\BIOSdata\F2G\F901318 [Redacted]
Author: [Redacted] Version Number: 3.0
Version Date: 06Apr2023
Template No.: CS_TP_BS016 Revision 6 Reference: CS_WI_BS005
Effective Date: 02Dec2019

F2G Ltd.
PROTOCOL F901318/0032

Visit windows are assigned based on the Protocol SOA are presented in below table. Assigned Visit

Assigned Visit	SOA day(s)	Study day(s)
V4 (Treatment)	3-5	3 to 5
V6 (Treatment)	6-8	6 to 8
V7 (Treatment)	9-11	9 to 11
V8 (Treatment)	14±2	12 to 16
V9 (Treatment)	17-18	17 to 18
V10 (Treatment)	21±2	19 to 23
V11 (Treatment)	24-25	24 to 25
V12 (Treatment)	28±2	26 to 30
V12a (Treatment)	35±2	33 to 37
V13 (Treatment)	42±3	39 to 45
V13a (Treatment)	49±3	46 to 52
V14 (Treatment)	56±3	53 to 59
V15 (Treatment)	70±3	67 to 73
V16 (Treatment)	84±6	78 to 90
V17 (Treatment)	EOT±3	-
V18 (Treatment)	Follow-up (4 wks after EOT ± 7d)	-
Derived EOT	84±6 or CRF EOT or last assessment done if CRF EOT is missing	78 to 90 or CRF EOT or last assessment done if CRF EOT is missing
Derived Day 84	84±6 or CRF EOT	78 to 90

Document: \\ieedc-vnasc01\BIOSdata\F2G\F901318 [Redacted]
 Author: [Redacted] Version Number: 3.0
 Version Date: 06Apr2023
 Template No.: CS_TP_BS016 Revision 6 Reference: CS_WI_BS005
 Effective Date: 02Dec2019

F2G Ltd.
PROTOCOL F901318/0032

Visit windows are assigned based on the Protocol SOA are presented in below table. Assigned Visit

Protocol SOA	SOA day(s)	Study day(s)
Start of Extended Treatment [ET]	Main Study Phase Day 85-91a	-
Extended Treatment	Every 4 weeks ± 7 days	-
End of Extended Treatment	-	-
Follow-up	4 weeks after End of Extended Treatment ± 7 days	-

a) The start of ET visit can be the same as the main study phase EOT/EOS visit at Day 84-90, but no later than Day 91. The first day of ET phase dosing will be the day after the last day of dosing in the main study phase.

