16.1.6. MISSING DATA METHODS FOR SECONDARY EFFICACY VARIABLES

16.1.6.1. DRC-adjudicated and Investigator-assessed overall response, clinical response, radiological response, mycological response

- Patients with a missing overall response at a specific visit will be considered as failures at the visit.

Document:	\\weedc-vnasc01\BIOSdata\F2G\F901318\		
Author:		Version Number:	3.0
		Version Date:	06Apr2023
Template No.:	CS_TP_BS016 Revision 6	Reference:	CS_WI_BS005
Effective Date:	02Dec2019		

F2G Ltd.
PROTOCOL F901318/0032

- Patients with a missing clinical response at a specific visit will be considered as failures at the visit.
- In cases where the radiological test was not done, or results are not available, or the test is not applicable/relevant, this information will appear as such in outputs. In cases where the radiological response is missing (and not captured in one of the before mentioned options), it will be indicated as “Missing” in tables.
- Patients with a missing mycological response at a specific visit will be assessed according to criteria in [Table D](#) as either presumed eradication (success), presumed persistence or no mycological follow-up results available (failure) at the visit.

Note: All mITT patients will be counted in the denominator of the %/ rate calculation at every visit through Day 84, even if they discontinue early. For mycological response, all patients with mycological evidence at baseline will be counted in the denominator of the %/rate calculation.

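### For EOT response endpoints, SAP 6.3 and 6.5 define derived EOT differently, and both can carry an older success forward against missing = failure

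*SAP*

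**What the plan says.** SAP 6.3 gives a narrow reason for a derived EOT: a patient still on drug at Day 84 may have only one of the Day 84 and EOT pages completed. Hence "a derived EOT assessment will be determined in order that all patients are included in summaries for EOT visit". The rule that follows applies to everyone: "Derived EOT visit is defined as the last non-missing measurement (including unscheduled measurements) which started after the first study medication administration", running "up to and including the last study medication administration on the main study phase".

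The window table in SAP 6.5 defines the same visit as "84±6 or CRF EOT or last assessment done if CRF EOT is missing". SAP 6.4 confirms that unscheduled data feed it: "Unscheduled measurements will not be included in by-visit summaries but will contribute to the derived EOT/EOS value".

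Derived EOT reaches the efficacy tables. The Derived Day 84 paragraph of SAP 6.3, which concerns all efficacy endpoints, ends "so that patients will be presented in summary tables at both Derived Day 84 and Derived EOT".

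Against this, SAP 16.1.6.1 says: "Patients with a missing overall response at a specific visit will be considered as failures at the visit". It has a matching line for clinical response. EOT is one of the listed visits for overall, clinical and mycological response (SAP 16.1.5.1 to 16.1.5.3 and 16.1.5.5). Protocol 6.3.1.5 also counts a patient without data at a visit as a failure.

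**The concern.** A rule that takes the last available on-treatment value is last observation carried forward. Missing = failure is the opposite convention. Both apply to the same cell of the same table, and the SAP does not clearly rank them. When the EOT response is missing, the carried value can only leave a failure as a failure or turn it into a success, so any bias runs one way.

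The two derived-EOT definitions also differ from each other. Two programmers following the SAP in good faith could therefore report different EOT response rates, by DRC and by Investigator.

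**Working it through.** The plan gives no EOT response rate and no EOT missingness, so there is no figure to reproduce. The check is a comparison of rules, followed by a scale calculation on stated assumptions.

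**Step 1: apply each rule to the same patient.** Each type below had an earlier on-treatment success, unless stated.

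| Patient | SAP 6.3 | SAP 6.5 | SAP 16 |
|---|---|---|---|
| A. Leaves for consent, AE or loss to follow-up; Day 28 success; no EOT response | success | success | failure (missing) |
| B. EOT page records failure 1-3 days after the last dose; Day 42 was a success | success (the EOT page is after the cut-off) | failure if the EOT page is used | failure (as recorded) |
| C. Day 28 success, dies on Day 30, no later assessment | success only if the derived value overrides Death | same | failure (Death is named) |
| D. Withdrawn from drug for an unsuccessful outcome | any older success is overridden by SAP 16 | same | failure at later timepoints |
| E. On drug at Day 84, only the Day 84 page completed | Day 84 response | Day 84 response | missing at EOT if read literally |

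A is the real conflict. B is the conflict between 6.3 and 6.5; it affects patients who do have EOT data and can run in either direction. C and D are settled by the response definitions, although the order of precedence is not written down. E is the case the derivation was meant to solve.

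Mycological response takes one more step. SAP 16.1.5.5 resolves a missing result through the clinical response at that visit. Type A patients have no clinical response at EOT, so they still end as failures there.

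**Step 2: effect of one re-scored patient.** The change in the EOT rate is 1/N.

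- N = 200 (anticipated enrolment): 1/200 = 0.5 percentage points.
- N = 100 (initial CSR): 1/100 = 1.0 percentage point.

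The actual denominator is the mITT set, which may be somewhat smaller.

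**Step 3: scale, on assumed inputs only.** Let m be the share of all patients of type A or similar with no EOT response, and s the share of those whose last on-treatment response was a success. The number re-scored is N × m × s. Assume m = 5-15%, s = 20-60%, and a 30% EOT success rate under missing = failure (60/200, Clopper-Pearson 95% CI 23.7-36.9%).

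- Low: 200 × 0.05 × 0.20 = 2 patients; 62/200 = 31%, a shift of 1 point.
- Middle: 200 × 0.10 × 0.40 = 8 patients; 68/200 = 34.0% (27.5-41.0%), a shift of 4 points.
- High: 200 × 0.15 × 0.60 = 18 patients; 78/200 = 39%, a shift of 9 points.

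At N = 100 the shifts in points are the same (1 to 9 patients). None of m, s or the 30% comes from the documents.

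**The case against.** The strongest reply has five parts.

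- **The protocol already defines EOT as a floating visit.** Protocol 8.2.1 takes it as the last assessment, scheduled or not, assigned to treatment. SAP 6.3 largely implements that, so the rule is not an invention. This stands, but 8.2.1 has no last-dose cut-off and does not set aside missing = failure.
- **SAP 7.2 refers missing efficacy data to section 16.** This favours reading section 16 as controlling. It does not close the matter, because a programmer can argue that a derived value is no longer missing.
- **Missingness should be limited.** EOT is required for all patients (Protocol Table 1, footnote b), and early leavers have EOT procedures (Protocol 4.3.4). This stands and argues against the upper end of the assumed range.
- **Both versions are visible.** SAP Appendix 1 lists CRF EOT and derived EOT as separate output visits. That helps, but the SAP never says which one is the secondary endpoint.
- **A strict rule could err the other way.** Under Protocol Table 1 footnote c, assessments from a visit within 1 week of EOT need not be repeated. Accepting only the EOT page could fail a patient who followed the protocol. This stands, and the fix must allow for it.

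A reader might also infer that deaths, or drop-outs in general, will be counted as EOT successes. The documents do not support that. Death is a named failure for overall, clinical and mycological response, and patients withdrawn for an unsuccessful outcome are failures from then on. Either could become a success only if a general visit-derivation rule overrode these specific definitions, and nothing in the SAP says that it does.

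**Conclusion.** The point holds for response at main study phase EOT, as a secondary endpoint only. SAP 6.3 and 6.5 disagree, and both allow an older on-treatment response to stand in for a missing EOT response that SAP 16.1.6.1 calls a failure. The exposed group is limited to patients who leave for other reasons, have no EOT response and had an earlier success. Separately, the 6.3 cut-off can replace a recorded EOT response with an older one.

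The size cannot be determined from the documents. What is firm is 0.5 points per patient at N=200 and 1.0 point at N=100. The range of 1 to 9 points rests wholly on assumed inputs and should not be read as an estimate. Nor should the point be extended to the main result: the primary endpoint is fixed at Day 42 and does not use derived EOT. The planned analyses are descriptive, so the consequence is an ambiguous and possibly favourable EOT rate, not a changed test result.

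**What to change.** Use one definition of derived EOT for response endpoints in SAP 6.3 and 6.5, applied in this order:

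1. The CRF EOT response if present, including one recorded after the last dose but within the EOT ±3 day window.
2. Otherwise, the response at a scheduled visit within 1 week of EOT, as Protocol Table 1 footnote c allows. This includes the Day 84-window page for patients still on treatment.
3. Otherwise, missing = failure.

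State that death on or before EOT, and prior withdrawal for an unsuccessful outcome, are failures at EOT whatever the derived value. Keep the last-non-missing rule for safety and EQ-5D-5L summaries; for response, use it at most as a labelled sensitivity analysis.

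The cost is a short SAP revision and one re-programmed derivation, using data already collected. The EOT rate may come out slightly less favourable.

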6.4. RETESTS, UNSCHEDULED VISITS AND EARLY TERMINATION DATA

In general, for by-visit summaries, data recorded at the nominal visit will be presented. Unscheduled measurements will not be included in by-visit summaries but will contribute to the derived EOT/EOS value, or best/ worst case value where required (e.g. shift table).

In the case of a retest (same visit number assigned), the latest available measurement for that visit will be used for by-visit summaries.

Listings will include scheduled, unscheduled, retest and early discontinuation data.

6.5. WINDOWING CONVENTIONS

Visit windows are assigned based on the

Protocol SOA are presented in below table. Assigned Visit

SOA day(s)	Study day(s)
V1 (Screening)	-7
V2 (Treatment)	1

Document: \\ieedc-vnasc01\BIOSdata\F2G\F901318 [Redacted]
Author: [Redacted] Version Number: 3.0
Version Date: 06Apr2023
Template No.: CS_TP_BS016 Revision 6 Reference: CS_WI_BS005
Effective Date: 02Dec2019

F2G Ltd.
PROTOCOL F901318/0032

Visit windows are assigned based on the Protocol SOA are presented in below table. Assigned Visit

Assigned Visit	SOA day(s)	Study day(s)
V4 (Treatment)	3-5	3 to 5
V6 (Treatment)	6-8	6 to 8
V7 (Treatment)	9-11	9 to 11
V8 (Treatment)	14±2	12 to 16
V9 (Treatment)	17-18	17 to 18
V10 (Treatment)	21±2	19 to 23
V11 (Treatment)	24-25	24 to 25
V12 (Treatment)	28±2	26 to 30
V12a (Treatment)	35±2	33 to 37
V13 (Treatment)	42±3	39 to 45
V13a (Treatment)	49±3	46 to 52
V14 (Treatment)	56±3	53 to 59
V15 (Treatment)	70±3	67 to 73
V16 (Treatment)	84±6	78 to 90
V17 (Treatment)	EOT±3	-
V18 (Treatment)	Follow-up (4 wks after EOT ± 7d)	-
Derived EOT	84±6 or CRF EOT or last assessment done if CRF EOT is missing	78 to 90 or CRF EOT or last assessment done if CRF EOT is missing
Derived Day 84	84±6 or CRF EOT	78 to 90

Document: \\ieedc-vnasc01\BIOSdata\F2G\F901318 [Redacted]
 Author: [Redacted] Version Number: 3.0
 Version Date: 06Apr2023
 Template No.: CS_TP_BS016 Revision 6 Reference: CS_WI_BS005
 Effective Date: 02Dec2019

F2G Ltd.
PROTOCOL F901318/0032

Visit windows are assigned based on the Protocol SOA are presented in below table. Assigned Visit

Protocol SOA	SOA day(s)	Study day(s)
Start of Extended Treatment [ET]	Main Study Phase Day 85-91a	-
Extended Treatment	Every 4 weeks ± 7 days	-
End of Extended Treatment	-	-
Follow-up	4 weeks after End of Extended Treatment ± 7 days	-

a) The start of ET visit can be the same as the main study phase EOT/EOS visit at Day 84-90, but no later than Day 91. The first day of ET phase dosing will be the day after the last day of dosing in the main study phase.

6.6. STATISTICAL TESTS

The default significance level will be (5%); 95% confidence intervals (CIs) will be presented and all tests will be two-sided, unless otherwise specified in the description of the analyses.

6.7. COMMON CALCULATIONS

For quantitative measurements, change from baseline will be calculated as:

- Test Value at Visit X – Baseline Value
- Percentage change from baseline will be calculated as:
- $([\text{Test Value at Visit X} - \text{Baseline Value}] / \text{Baseline Value}) \times 100$

6.8. SOFTWARE VERSION

All analyses will be conducted using SAS version 9.4 or higher. Non-compartmental PK parameter calculations will be performed using Phoenix® WinNonlin® 8.0 or higher ().

Document: \\ieedc-vnasc01\BIOSdata\F2G\F901318

Author:

Version Number:

3.0

Version Date:

06Apr2023

Template No.: CS_TP_BS016 Revision 6

Reference: CS_WI_BS005

Effective Date: 02Dec2019

7. STATISTICAL CONSIDERATIONS

7.1. MULTICENTER STUDIES

This study will be conducted by multiple investigators at multiple centres internationally. This is an open-label study, with no randomisation or stratification. Centre pooling will not be carried out for use in analyses for this study.

7.2. MISSING DATA

Summary statistics will be presented for observed data only. If a Baseline value is missing, no change from Baseline will be calculated. Missing data will be presented as part of a “Missing” category or statistic, if relevant.

Missing safety data will not be imputed.

Missing efficacy data will be handled as described in [section 16](#) of this SAP. Missing PK data will be handled as described in [section 17](#) of this SAP.

7.3. MULTIPLE COMPARISONS/ MULTIPLICITY

Not applicable.

7.4. EXAMINATION OF SUBGROUPS

The following subgroups will be presented for DRC-adjudicated overall response, Investigator-assessed overall response, and all-cause mortality. It should be noted that the study was not designed to detect treatment differences with high statistical power within subgroups, therefore this is a descriptive analysis only.

- 1) DRC-Adjudicated Baseline Disease Category and subcategory (patients may be included in more than one aspergillus subcategory)
 - Lomentospora (Scedosporium) prolificans (LoPro)
 - Scedosporium spp.
 - Aspergillus - All

Document: \\ieedc-vnasc01\BIOSdata\F2G\F901318\ [Redacted]
Author: [Redacted] Version Number: 3.0
Version Date: 06Apr2023
Template No.: CS_TP_BS016 Revision 6 Reference: CS_WI_BS005
Effective Date: 02Dec2019

F2G Ltd.
PROTOCOL F901318/0032

- Aspergillus - proven
 - Aspergillus - probable (IA-LRTD)
 - Aspergillus-R*
 - Aspergillus-S *
 - Aspergillus-unknown *
 - Coccidioides
 - Other F901318-susceptible fungi [this would include Fusarium, Phaeoacremon, Scopulariopsis, Histoplasmosis, Madurella, Sporothrix etc.]
- *To determine -azole resistance subcategory, consider the Central and Local Lab Microbiology Data for susceptibility result of 4 -azole drugs (itraconazole, voriconazole, posaconazole, isavuconazole) for the isolate;
 - If aspergillus is resistant to all 4 -azole then consider it as resistant
 - If at least one result is resistant then consider it as resistant
 - If all 4 are susceptible then susceptible
 - If no resistant and at least one susceptible then susceptible
 - If Intermediate and results awaiting then Unknown.

If the patient has a subcategory of “Unknown” using central lab data, or if central lab data was not available, the same criteria will be used to determine -azole resistance subcategory using local microbiology data. The following breakpoints were used to derive susceptibility result for aspergillus tested in the local lab, using MIC reported by the local lab:

- isavuconazole: resistant if MIC >1 ug/mL, susceptible if MIC <=1 ug/mL
- itraconazole: resistant if MIC >1 ug/mL, susceptible if MIC <=1 ug/mL
- posaconazole: resistant if MIC > 0.5 ug/mL , susceptible if MIC <=0.5 ug/mL
- voriconazole: resistant if MIC > 1 ug/mL, susceptible if MIC <=1 ug/mL
- If local MIC test is not available, a positive TR34/L98H test result would also indicate

Document: \\ieedc-vnasc01\BIOSdata\F2G\F901318 [Redacted]
Author: [Redacted] Version Number: 3.0
Version Date: 06Apr2023
Template No.: CS_TP_BS016 Revision 6 Reference: CS_WI_BS005
Effective Date: 02Dec2019

the isolate would be considered as resistant.

2) Prior antifungal therapy response

- Active (uncontrolled)
- Active (stable)
- Improved
- No therapy/Too brief

If the investigator has entered more than one response for prior antifungal therapy per patient, the worst outcome will be used (i.e. worst=refractory/failing, then stable/persistent, unable to judge, partial, complete)

3) Immunosuppression status

Each subject will be assigned one of 3 categories for immunosuppression status, based upon their underlying disease as completed by the Investigator at time of subject enrolment. Categories will be assigned as follows:

- Highly immunosuppressed will include subjects who have haematological malignancies or have received an haematopoietic stem cell transplantation.
- Moderately immunosuppressed will include subjects who either have immunological disorders (such as AIDS, chronic granulomatous disease and cystic fibrosis) or non-haematological malignancies or who have undergone solid organ transplant
- Low/no immunosuppression will include patients with any other underlying diseases and patients who are immunocompetent.

The immunosuppression category will be assigned as above by manual medical review of underlying disease terms prior to database lock, with appropriate documentation.

A second variant of immune status subgroup using two levels will to also be derived from the above:

- Low/No immunosuppression
- Moderate + High immunosuppression

4) Duration of prior antifungal therapy

Due to potential inconsistency of the investigator-entered categories in eCRF variable, duration of prior antifungal

Document: \\ieedc-vnasc01\BIOSdata\F2G\F901318\ [Redacted]
Author: [Redacted] Version Number: 3.0
Version Date: 06Apr2023
Template No.: CS_TP_BS016 Revision 6 Reference: CS_WI_BS005
Effective Date: 02Dec2019

F2G Ltd.
PROTOCOL F901318/0032

therapy (for systemic antifungal therapy received ≤ 14 days before first dose of study drug) will be calculated using start/stop date of antifungal therapy;

For any systemic antifungal therapy received ≤ 14 days before first dose, calculate total duration of exposure for the patient (i.e. stop date – start date + 1 for each antifungal therapy, and sum up total cumulative duration for the patient adding together exposure if more than one relevant antifungal or if antifungals overlap).

Patients will be assigned to subgroup category based on total cumulative duration;

- No prior antifungal therapy 2 weeks prior to study
- 1-7 days
- 8-14 days
- 15-28 days
- 29-90 days
- 91-180 days
- >180 days

Duration category of prior antifungal therapy entered into the eCRF by the investigator is available, but categories overlap and may not be accurate. Subgroup levels will be derived using start and stop dates entered into the eCRF for prior therapy.

Duration of prior antifungal therapy – two level

Using the same calculation as the duration of prior antifungal therapy above, patients will be assigned to a two-level subgroup category based on total cumulative duration;

- 0-28 days
- >28 days

Patients with no prior therapy will be included in the first level of the categories as “0 days”.

5) Malignancy type

Malignancy status will be derived for each patient based on primary underlying disease type entered into the eCRF,

Document: \\ieedc-vnasc01\BIOSdata\F2G\F901318 [redacted]
Author: [redacted] Version Number: 3.0
Version Date: 06Apr2023
Template No.: CS_TP_BS016 Revision 6 Reference: CS_WI_BS005
Effective Date: 02Dec2019

and medical review of malignancy type.;

- Haem-malignancy
 - Non haem-malignancy
 - No malignancy
 - Not applicable
- 6) Neutropenia status
- Neutropenia at screening
 - No neutropenia.

Patients who have neutropenia onset date within 28 days prior to first dosing (instead of any onset date prior to treatment start date) date and still ongoing at screening/baseline (i.e. not resolved prior to first dose date) will be categorised as “Neutropenia at screening”, otherwise patients will be categorised as “No neutropenia”.

7) Reason for Limited Treatment Options

Reason for Limited Treatment Options will be analysed as a 4-level variable for the subgroup analysis, by grouping the criteria for meeting limited alternative treatment options described in the Study Synopsis as follows:

- Known or predicted resistance to all licensed agents (including Known or predicted Resistance, Need oral – azole and -azole resistance is known, Need oral – azole and -azole resistance predicted by PCR, Need oral – azole and -azole resistance is predicted epidemiologically)
- Failure of available therapy (including Failure of available therapy, Inability to produce therapeutic drug levels, MM Approval.
- Intolerance to available therapy (including Intolerance to available therapy)
- Inability to manage DDIs (including Inability to manage DDIs, Need oral -azole Unmanageable azole DDI)

